4.1.2.1. Completion of Dose Escalation

No doses will be explored beyond 3.4 mg/kg, the dose that is considered to be the Maximum Feasible Dose (MFD).

4.2. Scientific Rationale for Study Design

Participants with RRMM who have experienced relapse after previous treatment with alkylators, PI and immunomodulatory imide drug represent a population of unmet

medical need in China, for whom there is no approved treatment options. Given the clinical activity demonstrated in the BMA117159 study, the treatment with belantamab mafodotin might offer a benefit to this participant population. It is also expected that due to its unique mechanism of action, belantamab mafodotin may be able to overcome the resistance to previously used drugs in the RRMM population in China.

BMA117159 study has evaluated the safety and tolerability of belantamab mafodotin at doses ranging from 0.03 mg/kg IV up to 4.6 mg/kg IV. Belantamab mafodotin was well tolerated with no DLTs up to 4.6 mg/kg q3w; MTD was not reached, however, there was limited tolerability of the 4.6 mg/kg dose (prolonged fever, headache, severe fatigue). The maximum clinical benefit (ORR 60%) was observed at the 3.4 mg/kg dose level, but a significant number of participants required dose delays and dose reductions. At lower dose levels, the results were variable, with wide confidence intervals. Based on these data, GSK has initiated Study 205678, a global phase II study evaluating the safety and efficacy of belantamab mafodotin monotherapy (3.4 and 2.5 mg/kg administered once every 3 weeks) in participants with relapsed / refractory multiple myeloma. As the safety profile of belantamab mafodotin is established in a predominantly Caucasian MM population, the primary objective of study 208465 is to evaluate safety and confirm appropriate dose for Chinese MM population. Given that there is no apparent evidence showing racial difference in MM and BCMA expression between Chinese and Western populations, global Phase II study selected dose (2.5 and 3.4 mg/kg) will be investigated in study 208465.

4.3. Justification for Dose

4.3.1. Belantamab Mafodotin Starting Dose Justification

The starting dose for belantamab mafodotin will be 2.5 mg/kg administered intravenously once every 3 weeks (Q3W) on Day 1 of each 21-day Cycle. The FTIH study tested doses up to 4.6 mg/kg, and global Phase II study selected 2.5 and 3.4 mg/kg for investigation in Study 205678. Currently there is no apparent evidence showing racial difference in MM and BCMA expression between Chinese and Western populations. However, PK difference may exist, as body weight usually affects clearance (CL) of monoclonal antibodies. Belantamab mafodotin dosing is adjusted by body weight. Thus, exposure difference is estimated low.

The starting dose is selected because of the following reasons.

- A starting dose lower than 2.5 mg/kg will have lower probability of getting clinical benefits based on the dose-response relationship in BMA117159. Also, the starting dose of 2.5 mg/kg had an acceptable safety profile in FTIH trial.
- De-escalation to 1.9 mg/kg will be allowed in case of \geq 2 DLT at dose 2.5 mg/kg.

Although AEs leading to dose reduction started from 0.96 mg/kg in BMA117159, careful dose escalation and monitoring will be implemented to ensure participants' safety throughout the study.

4.4. End of Study Definition

The end of study is defined as when all participants have progressed, died, withdrawn consent, discontinued treatment due to other reasons, or have been lost to follow-up.

A participant will be considered to have withdrawn from the study if any of the following apply:

- The participant is lost to follow-up.
- The participant has withdrawn consent.
- The participant is no longer being followed at the investigator's discretion.
- The study is closed or terminated.

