- 3. Belantamab mafodotin will be administered intravenously on Day 1 (D1) of every 21-day cycle until disease progression, death, unacceptable toxicity, withdrawal of consent or end of study.
- 4. The End of treatment (EOT) follow-up visit is to assess any residual AEs or toxicities associated with Study treatment. The visit should occur -within 45 days after last dose or before the start any new anti-cancer therapy.
- 5. PD follow-up once every 21 days: Participants who discontinue IP for a reason other than PD, disease evaluations will continue to be performed once every 21 days (±7 days) until confirmed PD, death, start of a new anticancer treatment, withdrawal of consent, or end of the study whichever occurs first.
- 6. Screening examination will be performed by an ophthalmologist (or an optometrist if an ophthalmologist is not available) within 21 days prior to first dose. See Section 8.3.9 for the list of ophthalmic exam procedures.
- 7. On-study ophthalmic exams to be performed by an ophthalmologist (or an optometrist if an ophthalmologist is not available) pre-dose every 3 weeks (schedule of assessment window should be within 5 days prior to dosing, all efforts should be made to schedule as close to dosing as possible). After the 6th dose of belantamab mafodotin (no schedule of assessment window needed): If there are no significant (Grade 2 or above) ocular symptoms or vision changes the frequency of ophthalmologic exams may be decreased to every 3 months until end of treatment. In case of persistent ocular exam findings, newly developed ocular symptoms or vision changes, further ocular exams should be performed at least every cycle until resolution (to Grade 1 or baseline) or more frequently as clinically indicated by the qualified eye care specialist (Appendix 9). See Section 8.3.9 for the list of ophthalmic exam procedures
- 8. Additional exams may be performed by the ophthalmologist (an optometrist if an ophthalmologist is not available), as clinically indicated.
- 9. If a participant's belantamab mafodotin dose is not administered at a given visit, the following activities do not need to be performed at that visit unless clinically indicated: ECG, weight, vitals, pregnancy test. Please follow the visit schedule in the SOA above, and perform these activities prior to a belantamab mafodotin infusion

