4. STUDY DESIGN

4.1. Overall Design

This is a phase I, open-label dose-escalation study to explore safety, PK, tolerability, immunogenicity and clinical activity of belantamab mafodotin monotherapy in Chinese participants with RRMM. The study will enroll up to 12 evaluable participants (For study schematic refer Figure 1). This study will include two dose cohorts. Up to six evaluable participants are expected for each cohort and the actual numbers will depend on the safety observed. Each participant will be involved in the study until participant have progressed, died, withdrawn consent, discontinued treatment due to other reasons, or have been lost to follow-up.

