6.6.1. Corneal Supportive Care Guidelines for Belantamab Mafodotin

Changes in visual acuity, which commonly manifests as changes in corneal epithelium observed on ocular examination, have been observed with antibody drug conjugates, including those conjugated to MMAF [Eaton, 2015].

Sites are required to establish a close collaboration with an ophthalmologist (or optometrist, if an ophthalmologist is not available) who will be responsible for assessing participants and managing those who develop corneal epithelium on ocular examination in close communication with GSK Medical Monitor.

Participants will be assessed by an ophthalmologist (or an optometrist if an ophthalmologist is not available) baseline and every three weeks. If there are no corneal examination findings (Grade 2 or above) at time of the Cycle 6 exam, participants may

have their ophthalmologic exams decreased to once every 3 months. In case of persistent ocular exam findings, newly developed ocular symptoms or vision changes, further ocular exams should be performed at least every cycle until resolution (to Grade 1 or baseline) or more frequently as clinically indicated by the qualified eye care specialist (Appendix 9). See Section 8.3.9 for the list of ophthalmic exam procedures.

Participants who have ocular symptoms at end of study treatment will continue to be followed as indicated in the SoA (Section 1.3) for up to 12 months, or until full resolution of findings: defined as a return to participant's baseline, or until deemed clinically stable by an ophthalmologist (or an optometrist if an ophthalmologist is not available), whichever comes first. Clinically stable is defined as changes less than or equal to Grade 1 as per Table 7.

Prophylactic preservative-free artificial tears should be administered in each eye at least 4 to 8 times daily, beginning on Cycle 1 Day 1 until EOT. Allow at least 5-10 minutes between administration of artificial tears and steroid eye drops (if administered). In the event of ocular symptoms (e.g., dry eyes), the use of artificial tears may be increased up to every 2 hours as needed.

While not yet clinically demonstrated, it is possible that the application of a cooling eye mask during belantamab mafodotin administration, and in the first few hours after infusion may subsequently decrease ocular side effects. On the day of infusion, at the discretion of the participant and the investigator, the following may be considered:

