7. DISCONTINUATION OF STUDY TREATMENT AND PARTICIPANT DISCONTINUATION/WITHDRAWAL

7.1. Discontinuation of Study Treatment

Participant will receive study treatment until disease progression, death or unacceptable toxicity (including but not restricted to meeting stopping criteria for significant toxicity as outlined in Section 6.6), loss to follow-up, or end of study (Section 4.4).

The study treatment must be permanently discontinued for any of the following reasons:

- disease progression or unacceptable toxicity (including protocol-defined safety stopping criteria)
- Pregnancy

Study treatment may be permanently discontinued for any of the following reasons:

- deviation(s) from the protocol
- request of the participant or proxy (withdrawal of consent by participant or proxy)
- Investigator's discretion
- concurrent illness that prevents further administration of study treatment(s)
- participant is lost to follow-up

study is closed or terminated.

The primary reason of study treatment was permanently discontinued must be documented in the participant's medical records and electronic case report form (eCRF).

If the participant voluntarily discontinues from treatment due to toxicity, AE must be recorded as the primary reason for permanently discontinuation on the eCRF.

Once a participant has permanently discontinued from study treatment, the participant will not be allowed to re-enter the study.

All participants who discontinue from study treatment for any reason other than confirmed progression or death will complete safety assessments, and will be followed up for PD after study as specified in the SoA (Table 1).

PD Follow-up:

All participants who permanently discontinue study treatment in the absence of disease progression will remain in the study and will be followed for progression according to the protocol schedule until:

- Progression is documented, or
- New anti-cancer therapy is initiated, or
- Lost to follow-up, or
- Withdrawal of consent, or
- Death occurs, or
- End of study (Section 4.4)

[figure not shown]

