3.2. Final Analyses

The final planned primary analyses will be performed after the completion of the following sequential steps:

1. All participants have completed the study as defined in the protocol, i.e., when all participants have progressed, died, withdrawn consent, discontinued treatment due to other reasons, or have been lost to follow-up.
2. All required database cleaning activities have been completed and final database release (DBR) and database freeze (DBF) has been declared by Data Management.

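### Section 4.1 ends involvement when treatment stops while Section 7.1 continues follow-up, and the end-of-study rule can cut that follow-up off

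*Protocol*

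**What the plan says.** **Participant level.** Protocol 4.1: "Each participant will be involved in the study until participant have progressed, died, withdrawn consent, discontinued treatment due to other reasons". Loss to follow-up completes the list. SAP 2.3 repeats this.

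**Study level.** Protocol 4.4: "The end of study is defined as when all participants have progressed, died, withdrawn consent, discontinued treatment due to other reasons". Loss to follow-up again completes the list. A separate list in 4.4 says who counts as withdrawn from the study. Stopping treatment is not on it.

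**Final analysis.** SAP 3.2 takes study completion from the protocol, that is, "when all participants have progressed, died, withdrawn consent, discontinued treatment due to other reasons, or have been lost to follow-up". Protocol 9.5 uses the same list.

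**Follow-up after stopping without progression.** Protocol 7.1: "All participants who permanently discontinue study treatment in the absence of disease progression will remain in the study and will be followed for progression". Footnote 5 of the Schedule of Activities: "Participants who discontinue IP for a reason other than PD, disease evaluations will continue to be performed once every 21 days", with a window of ±7 days. Both places also list end of study as a stop for this follow-up, and 7.1 refers to Section 4.4 for its meaning.

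**Other windows after treatment.** Footnote 4 places the end-of-treatment visit within 45 days of the last dose or before new therapy. Protocol 8.3.1 collects adverse events until 70 days after discontinuation, and SAP 14.4.2 uses 70 days after the treatment stop date to flag treatment-emergent events.

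**The concern.** Two rules about the same person disagree. A participant who stops for toxicity is out of the study under 4.1 and still in it under 7.1, so a site cannot tell whether the 21-day evaluations are owed.

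The study-level rule adds a second problem. Stopping treatment counts towards end of study, and end of study closes the follow-up that stopping treatment was meant to open. Duration of response (Protocol 9.4.9, SAP 7.2) runs from first response to progression or death due to progression. A responder who stops without progression can therefore lose the progression date because of how the study end is worded. SAP 7.2 states no censoring rule for such a responder, so the cut-off would not be handled explicitly.

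The trigger also takes no account of the adverse-event window. The number of participants with adverse events is part of the primary endpoint, and the condition for the final analysis can be met before that window has run out for the last participants treated.

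**Working it through.** The plan gives no figure to reproduce on this point. The check sets the rules side by side and then follows the dates.

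**Status of participant A, who stops without progression while B is still on treatment**

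| Rule | A's status |
|---|---|
| Protocol 4.1, SAP 2.3 | Involvement over |
| Protocol 7.1, footnote 5 | In the study, evaluated every 21 days |
| Protocol 4.4, withdrawal list | Not withdrawn |
| Protocol 4.4, end-of-study list; 9.5; SAP 3.2 | Counts as completed |

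The direct contradiction is between 4.1 and 7.1. The withdrawal list in 4.4 supports 7.1.

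**When B also stops without progression, on day X**

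1. Every participant now meets an item in the 4.4 list, so end of study is day X.
2. Section 7.1 and footnote 5 stop progression follow-up at end of study, so follow-up may close on day X for both A and B.
3. Protocol 9.5 and the first condition in SAP 3.2 are met on day X.

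**What is still outstanding on day X.** Assume B's discontinuation is dated d days after the last infusion, with d between 0 (same day) and 21 (the next planned dosing day).

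- Latest end-of-treatment visit: 45 − d = 45 to 24 days after X.
- Adverse-event collection under Protocol 8.3.1, counted from discontinuation: 70 days after X.
- Treatment-emergent window under SAP 14.4.2, if the stop date is the last infusion: 70 − d = 70 to 49 days after X.
- First progression follow-up visit, if counted from X: 21 ± 7 = 14 to 28 days after X.

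All four fall after the trigger, and B could have no progression follow-up visit at all.

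**Does other text repair this?** SAP 14.7.1 defines participant completion as all scheduled visits plus an exit visit, but SAP 3.2 spells out the 4.4 list instead. The second condition in SAP 3.2, database cleaning and release, will take time in practice but names none of these windows.

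**Who is exposed.** The design allows 2 cohorts × 6 = 12 evaluable participants. The Amendment 3 rationale says two were still on treatment and benefitting. Their discontinuation could set day X.

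**The case against.** The strongest reply is that 4.4 is a deliberate administrative cut-off. It is a study-level rule, 7.1 and footnote 5 both name end of study as a stop, and the amendment summary says the definition was chosen to match other oncology protocols. Someone who stops early is still followed while another participant remains on treatment. The study is descriptive, duration of response is not among its listed primary or secondary endpoints (the exploratory rows are redacted), and censoring a few responders leaves dose decisions untouched.

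Much of this stands. A reader might infer that 4.4 contradicts 7.1. It does not, because 7.1 defers to it. What remains is the 4.1 conflict, the truncation that 4.4 and 7.1 produce together, and a final-analysis trigger that does not wait for windows the protocol itself requires. Nothing in the documents says this last effect was intended.

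Three stronger readings should not be drawn:

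- **Ocular follow-up is closed too.** Section 6.6.1 runs it "for up to 12 months, or until full resolution of findings", or until clinical stability, and lists no end-of-study stop. Footnote 37 continues contact after discontinuation until visual symptoms resolve. Section 8.3.3 follows adverse events of special interest, which include corneal events, to resolution, stabilisation, other explanation or loss to follow-up.
- **The response rate will fall.** A first response left unconfirmed would become not evaluable under SAP Table 1, moving the rate by 1/6 = 16.7 points with 6 treated or 1/12 = 8.3 points with 12. But the end-of-treatment visit includes response assessment, and note 1 to that table needs only a later adequate assessment from a different sample, with no minimum interval. Long-treated participants are unlikely to be at a first, unconfirmed response. The loss is possible but unlikely, and needs the end-of-treatment assessment to be missing.
- **The 10% discontinuation rate for adverse events in Section 2.3.2 sizes the problem.** It gives the chance that someone stops for an adverse event. Truncation also needs that person to be progression-free when the last treated participant stops.

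**Conclusion.** The point holds. Section 4.1 and SAP 2.3 contradict Section 7.1 and footnote 5. Separately, the rules in 4.4, 9.5 and SAP 3.2, read literally, end the study and permit the final analysis on the day the last treated participant stops without progression. Duration of response is then cut short for anyone still progression-free. The trigger can fall up to 45 days before the last end-of-treatment visit and up to 70 days before adverse-event collection is due to finish.

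The documents do not allow a probability to be put on this. The truncation rests on at least one participant being progression-free when the last treated participant stops. The adverse-event gap rests on the trigger being applied as worded. Section 8.3.1 has no end-of-study stop, so collection itself is not switched off; the trigger simply does not wait for it. With so few participants, each progression date matters to a descriptive summary.

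**What to change.** 1. In Protocol 4.1 and SAP 2.3, state that participants who stop treatment without progression remain in progression follow-up as described in Section 7.1.
2. In Protocol 4.4, Protocol 9.5 and SAP 3.2, replace the item on stopping treatment for other reasons with completion of the end-of-treatment visit, the 70-day adverse-event collection and progression follow-up. Progression follow-up ends at progression, death, new anti-cancer therapy, withdrawal of consent or loss to follow-up. Word it so that the visit and the 70 days also apply to participants who stop at progression; otherwise the adverse-event gap remains for them.
3. In Protocol 7.1 and footnote 5 (reproduced in SAP 14.2), reconcile the end-of-study stop so that the definition is not circular, for example by limiting it to sponsor closure or a stated maximum follow-up.
4. While these sections are open, align the completion definition in SAP 14.7.1 and state the censoring rule for duration of response in SAP 7.2.

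**Cost.** These are wording changes, and the visits are already scheduled. The real cost is time. Closure and the final analysis, including the primary safety analysis, could move by many months for a durable responder: Section 2.3.1 cites a median duration of response of 11.0 months at 2.5 mg/kg with the upper limit not reached. Each extra year is about 365/21 ≈ 17 evaluation visits per participant. A stated maximum follow-up would cap this.

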The protocol has been amended to accommodate the updates based on latest information available through investigator's brochure. The study period was extended to maintain the study treatment of two ongoing participants who are benefitting from the Belantamab mafodotin treatment as judged by investigator.

Section # and Name	Description of Change	Brief Rationale
Section 1.1. Synopsis Section 5.1. Inclusion criteria	Inclusion criteria 8 and 9: Updated the period to use contraception (Female: 4 months after last dose of belantamab mafodotin; Male: 6 months after last dose of	Updated based on current safety information
Section 1.3. Schedule of Activities (SoA)	belantamab mafodotin) Updated footnote 19 and 33 - Samples for pharmacokinetics will be collected for the interpretation of ADA results one year after the first dose of last subject - Samples for CI will be collected up to one year after last subject first dose	As the sample for pharmacokinetic analysis and color will not be collected further.
Section 2.2. Background	Current treatment landscape for treating Relapsed/Refractory Multiple Myeloma (RRMM) in China	Updated based on latest information available
Section 2.3.3. Pharmacokinetics and Pharmacodynamics	Pharmacokinetic and Pharmacodynamic information updated	Updated to align with current IB information
Section 2.4.1. Risk Assessment	Update in explanation of risks	To align with IB update
Section 2.4.3. Overall benefit: Risk conclusion	Removed the clinical experience available from the study BMA117159	Based on current safety information
Section 3. Objectives and Endpoints	Added exploratory objective and endpoint for CCI assessment	To align with Schedule of activities table

Section # and Name	Description of Change	Brief Rationale
Section 4.1. Overall Design Section 4.4. End of study	Updated or added the definition of End of study (EOS)	To make it align with other study protocols in oncology

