Section 6.6. Dose modification	Updated Table 5 Dose Modification Guidelines for Belantamab Mafodotin- Related Adverse Events. - Added row for 'Urine Dipstick'. - For thrombocytopenia separate recommendations are made for Belantamab Mafodotin during grade 3 and grade 4 toxicity - For Neutropenia, recommendations for Belantamab Mafodotin are updated according to current available information - For Pneumonitis, recommendations for Belantamab Mafodotin for Grade 2 and Grade 3-4 toxicities are updated according to current available information	Updated based on current information on BCMA
Section 7.1. Dose modification	Added a point that study treatment may be permanently discontinued at 'Investigator's discretion'.	Added for clarity
Previous Sections 7.1.2. QTc Stopping Criteria	Deleted	Based on available data, cardiac risk was determined to be low and stopping criteria were removed
Previous Sections 7.1.4. Left Ventricular Ejection Fraction (LVEF) Stopping criteria	Deleted	Based on available data, cardiac risk was determined to be low and routine monitoring was removed
Section 8.3.1. Time Period and Frequency for Collecting AE and SAE Information	SAE and AE collection period has been updated from 45 days to 70 days after the participant is discontinued from the study treatment.	Updated as per current safety information
Section 9.4.9. Clinical Activity Analyses	Added CCI assessment	To align with updated objective and endpoint
Section 9.5. Interim Analyses	Updated end of study definition	To align with updated EOS definition in Section 4.4
Section 11.2. Appendix 2. Clinical Laboratory Tests	Added point number 6, on use of urine dipstick to assess for presence of urine protein	Added for clarity
Section 11.4. Appendix 4. Contraceptive Guidance and Collection of Pregnancy Information	Under heading: Collection of Pregnancy Information. The duration is updated from 5 months to 6 months for pregnancy information of a female partner of a male study participant following last dose of study treatment.	Updated according to current safety information

Section # and Name	Description of Change	Brief Rationale
	The duration is updated from 8 months to 4 months for pregnancy information of a female study participant following last dose of study treatment.	
Whole document	Minor editorial, alignment for consistency and document formatting revisions	Minor, therefore not been summarized

TABLE OF CONTENTS

			PAGE
PR	OTOC	OL AMENDMENT SUMMARY OF CHANGES TABLE	3

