8.3.1. Time Period and Frequency for Collecting AE and SAE Information

- All SAEs will be collected from signing of the ICF until 70 days following discontinuation of study treatment regardless of initiation of a new cancer therapy or transfer to hospice at the time points specified in the SoA (Table 1). However, any SAEs assessed as related to study participation (e.g., study intervention, protocol-mandated procedures, invasive tests, or change in existing therapy) or related to a GSK product will be recorded from the time a participant consents to participate in the study up to and including follow up.
- All AEs will be collected from the start of treatment until 70 days following discontinuation of study treatment regardless of initiation of a new cancer therapy or transfer to hospice at the time points specified in the SoA.
- Medical occurrences that begin before the start of study treatment but after obtaining informed consent will be recorded on the Medical History/Current Medical Conditions section of the electronic case report form (eCRF) not the AE section.
- All SAEs will be recorded and reported to the sponsor or designee immediately and under no circumstance should this exceed 24 hours, as indicated in Appendix 3. The investigator will submit any updated SAE data to the sponsor within 24 hours of it being available.
- Investigators are not obligated to actively seek AEs or SAEs in former study participants. However, if the investigator learns of any SAE, including a death, at any time after a participant has been discharged from the study, and he/she considers the event to be reasonably related to the study treatment or study participation, the investigator must promptly notify the sponsor.

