14.4.2. Treatment Emergent Flag for Adverse Events

Flag	Definition
Treatment Emergent	
• Study Treatment Start Date ≤ AE Start Date ≤ Study Treatment Stop Date + 70 days.

NOTES:

- If the study treatment stop date is missing, then the AE will be considered to be On-Treatment.
- Time of study treatment dosing and start/stop time of AEs should be considered, if collected.

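### AEs count to 70 days after treatment, but no general AE contact is scheduled after EOT for participants who progress or start new therapy, and the study can end inside that window; pregnancy windows also conflict

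*Protocol*

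**What the plan says.** **AE window.** Protocol 8.3.1 states: "All AEs will be collected from the start of treatment until 70 days following discontinuation of study treatment". SAEs run to the same day, and neither stops when new therapy begins. SAP 14.4.2 flags an AE as treatment-emergent if it starts no later than "Study Treatment Stop Date + 70 days". SAP 14.4.1 takes the stop date from the exposure records.

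**Visits after treatment.** SoA footnote 4 makes EOT the visit for residual AEs: "The visit should occur -within 45 days after last dose or before the start any new anti-cancer therapy". Footnote 5 then limits who is seen again: "Participants who discontinue IP for a reason other than PD, disease evaluations will continue to be performed once every 21 days", and only "until confirmed PD, death, start of a new anticancer treatment, withdrawal of consent, or end of the study whichever occurs first". Footnote 36 carries related SAEs, not AEs in general, through PD follow-up.

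**End of study.** Protocol 4.4 states: "The end of study is defined as when all participants have progressed, died, withdrawn consent, discontinued treatment due to other reasons", or been lost to follow-up. Section 9.5 ties the final analysis to the same event. SAP 3.2 adds database cleaning, release and freeze, without a minimum interval.

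**Pregnancies.** Section 8.3.5 collects them for 8 months after last dose in female participants and 5 months in partners of male participants. SoA footnote 16a asks for a test at 8 months, and SAP Appendix 2 repeats it. Protocol Appendix 4, to which 8.3.5 sends sites for procedures, says 4 and 6 months. Inclusion criteria 8 and 9 require contraception for 4 months (female) and 6 months (male).

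**The concern.** Safety is the primary objective, and the percentage of participants with AEs is part of the primary endpoint. The plan sets a 70-day window for collecting and counting events, but the visit schedule does not reach its end for two groups: those who stop because of progression, and those who start new therapy. Nothing fixed prompts the site to ask about an AE or SAE that begins late in the window. The end-of-study rule compounds this for the last participants, because it can be met while their window is still open.

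Late SAEs and maximum grade are the summaries most exposed. The pregnancy conflict is separate: sites have two current rules. Under 8.3.5 read alone, a partner pregnancy in month 6 would not be collected although male contraception is still required then.

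**Working it through.** The plan gives no figure of its own to reproduce here, so the check is day arithmetic on its stated windows. Two clocks are in play and are labelled throughout: **last dose** (EOT timing and the SAP's exposure dates) and **discontinuation** (8.3.1).

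**1. Days without a scheduled general AE contact, from last dose.** EOT is credited as an AE contact, as footnote 4 describes it. Gap = 70 − EOT day.

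| EOT day | Source | Gap | Share of 70 days |
|---|---|---|---|
| 45 | latest day in footnote 4 | 70 − 45 = 25 | 35.7% |
| 30 | assumed, e.g. before new therapy | 70 − 30 = 40 | 57.1% |
| 21 | assumed | 70 − 21 = 49 | 70.0% |

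On the 8.3.1 clock, if discontinuation comes *d* days after last dose, the window ends on day 70 + *d* and the gap after a day-45 visit is 25 + *d*. So 25 days is the minimum on either clock.

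**2. Days of the last participant's window left when 4.4 is met, from last dose.** Remaining = 70 − day of the event.

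- Progression found at the next 21-day visit (assumed), with the ±3-day window, is day 18 to 24: 70 − 24 = 46 to 70 − 18 = 52 days left.
- PD confirmed 14 days after a day-21 finding is day 35: 70 − 35 = 35 days left.
- Progression more than 70 days after last dose, for instance after a long dose hold: none left.

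On the discontinuation clock the upper bound is 70 days, when 4.4 is met on the day the last participant discontinues. That is 70/7 = 10 weeks, the most a floor could delay the freeze.

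**3. Why the clock matters.** The collection window (discontinuation + 70) and the counting window (last exposure + 70) differ by the *d* days between last dose and discontinuation. Events in those final days are collected but not flagged. Long holds are plausible: Protocol 2.3.2 reports a median of 91 days (range 21 to 201) for corneal findings to resolve in the phase II study at 2.5 mg/kg. As an illustration, after a 91-day hold followed by discontinuation, last dose + 70 would already have passed by 91 − 70 = 21 days.

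**4. Effect on a percentage.** In a full cohort of six, one participant is 1/6 = 16.7 points. A missed late SAE moves the SAE percentage by that amount only if the participant had no earlier SAE.

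**5. Pregnancy windows, months after last dose.**

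| | 8.3.5 | Appendix 4 | Difference | Contraception |
|---|---|---|---|---|
| Female participant | 8 | 4 | 8 − 4 = 4 | 4 |
| Partner of male participant | 5 | 6 | 6 − 5 = 1 | 6 |

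Appendix 4 agrees with the contraception periods in both rows; 8.3.5 agrees in neither.

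**The case against.** **The duty to collect exists.** Section 8.3.1 obliges sites to collect to day 70 whatever the SoA schedules. This stands. A reader might infer that AE collection stops at EOT or progression; the text does not say so. What is missing is a scheduled contact. The same section does not require active searching in former participants, and 4.1 describes involvement as ending at progression, so the duty alone is a weak prompt.

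**Late SAEs have other routes.** Investigators must report related SAEs they learn of after discharge (8.3.1), and Protocol 11.3.5 allows paper reporting once the electronic tool is off-line. These reduce the risk, but they do not ensure that events are sought or reach the frozen database.

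**Follow-up of known events is protected.** A reader might infer that closure cuts short open SAE, AESI or ocular follow-up. The documents do not support that. Section 8.3.3 follows SAEs and AESIs to resolution, stabilisation, other explanation or loss to follow-up, without naming end of study as a stopping point. Section 6.6.1 allows up to 12 months of ocular follow-up, and footnote 37 continues visual follow-up after discontinuation. The point is confined to detecting new events.

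**Footnote 4 is not an AE cut-off.** It sets a visit window. The amendment summary records that "SAE and AE collection period has been updated from 45 days to 70 days", which might suggest an overlooked update, but that is background only. The mismatch rests on current text.

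**Completion may mean more than 4.4.** SAP 14.7.1 ties participant completion to all scheduled visits plus an exit visit. Even so, no visit is scheduled at day 70, so a day-45 EOT still leaves 25 days. Cleaning takes time in practice, but no minimum is set.

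**Reach is small.** The Amendment 3 rationale says: "The study period was extended to maintain the study treatment of two ongoing participants". This stands and limits the size of the point.

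**Conclusion.** The point holds as a mismatch between the AE window and the schedule meant to serve it. For participants who stop at progression or start new therapy, at least 25 of 70 days from last dose (36%) have no scheduled general AE contact, and more if EOT is earlier. End of study can be met with about 46 to 52 days left if progression is found at the next visit, about 35 if PD is confirmed 14 days later, and none on the last-dose clock after a long hold. These closure figures depend on the assumed event dates and concern only the last participants to finish.

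The DLT endpoint, confined to Cycle 1, is unaffected, and the effect on AE percentages is probably small. A 17-point shift in the SAE percentage is possible in a cohort of six only for a participant with no earlier SAE. That condition matters, since Protocol 2.3.2 reports SAEs in 41% of the pooled 2.5 mg/kg cohort.

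The pregnancy conflict is certain on current text but changes no table, because SAP 8.6 plans narratives only. The changes should be made, because they are cheap and protect safety ascertainment for the primary objective.

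**What to change.** (a) Add to the SoA a telephone AE contact at day 70 after discontinuation for any participant with no visit at that time.

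(b) Keep the 8.3.1 clock at discontinuation. Moving it to last dose would shorten collection after a dose hold. Instead, make the stop date in SAP 14.4.1 and 14.4.2 consistent with 8.3.1.

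(c) State in Protocol 4.4 and 9.5 and SAP 3.2 that end of study and database freeze cannot precede the end of the last participant's 70-day AE window.

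(d) Align 8.3.5 and SoA footnote 16a, with its copy in SAP Appendix 2, to Protocol Appendix 4: 4 months for female participants, 6 months for partners.

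Cost: wording, one call per affected participant (about two still on treatment when Amendment 3 was written, plus anyone still in their window), and a freeze up to about 10 weeks later. The late part of the window would then close with a scheduled contact.
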